Previously, we have examined the relationship between trauma and adverse outcomes but have not specifically focused on older patients ²⁰⁻²². It is possible that the immune systems of older patients react differently to injury when compared to younger cohorts, and this may increase vulnerability to MODS ^{14,23,24}. Decreased skeletal muscle mass in older people is reported to impair immune system function in intensive care patients²⁵ and severe injury may further alter immune cell activity, causing physiological changes leading to adverse outcomes^{26,27}. Altered metabolism after trauma is associated with increased inflammatory responses²⁸ and together with the nutritional deficits observed in critically injured older people²⁹ these may contribute to age-related MODS. Frailty is also known to reduce physiological function ^{30,31} and frailty in older people independently predicts in-hospital complications such as pneumonia or deep vein thrombosis after injury ³². Therefore it may be that frailty rather than age increases the risk of MODS after severe injury. Previous trauma studies suggest that both older age and frailty are associated with decreased longer-term independence after injury ^{32,33}. However the impact of MODS on longer-term function, dependence and recovery in older people has not been investigated. The lack of UK-based evidence means that the prevalence, predictors and outcomes of MODS in our older trauma patients are unknown.

This prospective observational study will evaluate the patterns of MODS in trauma patients and determine to what extent it is related to ageing and frailty. By understanding specific age-related predictors or drivers of MODS we aim to identify treatment or prevention strategies which will enhance recovery for severely injured older people. MODS is also associated with late, indolent death, and by studying patterns of this mortality in older patients we may be able to prognosticate futility. This may enable stratification of older patients most likely to respond to intervention and those who would benefit from supportive or palliative care. Finally, evidence of how MODS impacts longer-term recovery and quality of life will support rehabilitation practice, and where appropriate, self-managed recovery for older trauma patients and their support networks.

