5. STUDY OBJECTIVES

This study aims to:

- Identify the prevalence, severity and patterns of MODS in older patients
- Determine predictors and risk factors of developing MODS for older patients
- Identify age related characteristics that contribute to MODS
- Examine the mode of mortality associated with MODS
- Analyse the relationship between MODS and longer-term recovery and quality of life for older patients

The primary outcome is the presence of MODS during the critical care admission period. An individual Sequential Organ Failure Assessment (SOFA) score of 1 in any organ represents dysfunction. Multiple organ dysfunction syndrome (MODS) is defined as a total daily SOFA score of >5.

Secondary outcomes are in-hospital mortality, ventilator use, level of organ support, adverse events such as infection or stroke, critical care stay and total length of stay. Longer terms outcomes are quality of life and recovery at one year post injury.

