6. METHODOLOGY

Study Design

This is a pan-London prospective observational study which aims to characterise organ dysfunction in older trauma patients \geq 65 years. All adults admitted to an adult critical care unit within one the London Major Trauma Centres (MTCs) will be considered for enrolment, with younger patients (<65 years) recruited as a control group.

Settings

There are four MTCs in London. Each site will have a nominated Principal Investigator (PI). Organ injury scoring training will be provided for local research nurses or data collectors prior to study commencement. Two funded research nurses from Queen Mary University of London (QMUL) will support patient enrolment, data collection and data quality monitoring across the four MTCs. Each site will be supported by an on-line information folder with the protocol, guidance/explanatory notes and contact details of the Principal Investigator. For this study, a critical care unit is defined as either an Intensive Care Unit (Level 3 care) or a combined unit of Intensive Care (Level 3 care) and High Dependency Unit (Level 2 care).

Inclusion Criteria

- Adult major trauma patients (≥16 years of age) admitted to adult critical care within one of the four London Trauma System MTCs. This includes direct admissions from the Emergency Department, admissions from the operating theatre or from a ward, transfers from other facilities and readmission to critical care.

Exclusion Criteria

- Patients with a burns-only injury
- Patients who are prisoners
- Patients who decline to provide informed consent or do not have consultee consent

Study Design / Plan – Study Visits

Trauma patients (≥16 years of age) admitted to MTC critical care during the enrolment phase of the study (two years in total) will be identified by the local PI together with clinical care staff. The local PI will be responsible for ensuring patient enrolment, participant consent, data collection, patient detail de-identification, data entry and storage. Data from routine clinical care records will be recorded daily by local and QMUL research nurses whilst the patient is admitted to the critical care unit.

The clinical data collection will include:

- Demographics: Age within a range, gender, co-morbid disease, pre-injury medication
- Injury variables: Mechanism of injury, Injury Severity Score (ISS)
- Organ dysfunction: The frequency, pattern and severity will be measured daily using Sequential Organ Failure Assessment (SOFA) scoring

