- Total number of days on organ support (CTCOFR score)
- Immune cell function: Daily clinical measures of lymphocyte and neutrophil counts
- Adverse events: Such as infection, delirium, stroke or cardiac dysfunction
- Nutrition: Nutritional requirements, nutrition intake and weight measurements
- Frailty screening using the Edmonton Frail Scale (https://www.nscphealth.co.uk/edmontonscale-pdf)
- Length of stay: In critical care and total hospital stay
- Mortality: Mode and timing

[figure not shown]
As soon as clinically appropriate (determined by the clinical care team in charge of the patient), consent will be sought for inclusion of data into the study and long term follow up. If the patient remains incapacitated due to injury or treatment, consent will be sought from a personal or nominated consultee.

At 12 months post injury patients will be approached by letter, email or telephone (according to patient wishes) and health-related quality of life and longer-term recovery data will be collected using the EuroQol-5D (EQ5D) questionnaire. This was chosen as it has been previously validated to capture outcomes in trauma patients including older people and takes approximately 15 minutes to complete.

Study Scheme Diagram

Each MTC will be identified by a number rather than name.

Eligible trauma patients admitted to the critical care unit during the study period will be identified by the clinical care team.

The PI and research nurses have responsibility to ensure patient anonymity is protected and maintained. They will also ensure that patient identities are protected from any unauthorised parties. Information regarding study patients will be kept confidential and managed in accordance with the Data Protection Act, NHS Caldicott Guardian, The Research Governance Framework for Health and Social Care and Research Ethics Committee Approval.

Although patient identifiable data will be available to research staff they will not be entering it on to the paper case record form (CRF). The de-identified data required for this study is already recorded as part of routine clinical care and as part of the Intensive Care National Audit and Research Centre (ICNARC) audit. Organ failure scoring is not usually conducted as part of routine clinical care however it uses parameters that are recorded by critical care clinical staff on a daily basis.

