Univariate analysis of variables between the two age groups (< 65 years and ≥65 years) will be conducted using unpaired students t-tests or Mann Whitney U tests (for parametric and non-parametric data respectively). Analysis of more than two groups (for example thresholds of immune counts or degrees of organ dysfunction) will be conducted using ANOVA or Kruskal Wallis tests. Chi-squared statistic or Fisher's exact tests will be used to compare proportions of MODS between the two cohorts.

Multivariable regression analysis will be used to determine statistically independent relationships between MODS and age plus other significant independent variables (such as the effect of injury severity, blood transfusion, on the development of MODS). Multivariate linear regression will be used to analyse continuous dependent variables and binary logistic regression for binary dependent variables. Results of linear regression will be reported as Beta co-efficient with 95% confidence intervals, and for logistic regression adjusted Odds ratios (OR) with 95% confidence intervals.

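### MODS is fixed once over the whole critical care stay, and the named methods ignore its onset, so any comparison of stay or timing of death by MODS is open to immortal-time bias

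*Protocol*

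**What the plan says.** Section 5 (Study Objectives) sets the outcome window: "The primary outcome is the presence of MODS during the critical care admission period". The threshold is given there too: "Multiple organ dysfunction syndrome (MODS) is defined as a total daily SOFA score of >5". No minimum duration and no onset window is stated. Each patient therefore has one status, and a single qualifying day at any point in the admission is enough.

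Section 6 (Study Visits) says when scores exist. Clinical data are "recorded daily by local and QMUL research nurses whilst the patient is admitted to the critical care unit", so the days on which a patient can qualify are the days of that patient's stay.

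MODS is not only an outcome. One objective in section 5 is to "Examine the mode of mortality associated with MODS". The Introduction says: "MODS is also associated with late, indolent death, and by studying patterns of this mortality in older patients", and connects this with judging when treatment is futile. Section 6 lists "Mortality: Mode and timing" among the data collected, together with days on organ support. The secondary outcomes in section 5 include "critical care stay and total length of stay".

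The synopsis places ANOVA and Kruskal-Wallis tests for more than two groups under secondary outcome analysis. Section 6 (Methods of analysis) gives an example of such groups: "degrees of organ dysfunction) will be conducted using ANOVA or Kruskal Wallis tests". For regression it names linear models for continuous outcomes and logistic models for binary ones. It names no time-to-event, time-varying, landmark or competing-risk method.

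**The concern.** MODS is a state that a patient enters on some day. A label that records whether it was ever entered during the stay depends partly on how long the stay was. A patient who leaves or dies on day 2 has had two chances to be labelled; one who stays 20 days has had twenty. If the label is then used as though it were known at admission, the days before onset, on which the patient had by definition not yet left or died, are credited to MODS. The same happens with a graded score if its highest value over the stay is used, since a maximum tends to rise with the number of days scored.

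The direction matters here. The artefact is longer stay and later death with MODS, which is the pattern that the Introduction expects. A false result would look like confirmation, and it could feed into the prognostic use the Introduction describes for older patients.

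**Working it through.** The protocol states no figure for this point. The check asks how large a difference the labelling alone produces when MODS has no effect on discharge or death.

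**Input from the protocol.** MODS rates of 33% in 518 older and 23% in 828 younger patients (section 6, Sample size). The overall rate is (518 × 0.33 + 828 × 0.23) / 1346 = 361.4 / 1346 = 26.8%. The calculation below uses P = 26.5%.

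**Assumptions, not in the protocol.**
- Mean critical care stay *m* = 8 days, with 5 and 12 as alternatives.
- Constant daily chance of leaving the unit, g = 1/m.
- 15% of exits are deaths.
- A share *f* of MODS cases is present on day 1. The rest arise from day 2 with a constant daily chance *h*, independent of exit.

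**Formulas.**
- Patients with MODS on day 1: a = P·f.
- Chance of later MODS among the others: q = (P − a)/(1 − a).
- Daily onset chance that gives q: h = q·g / [(1 − g)(1 − q)].
- Daily chance of leaving or qualifying: r = g + (1 − g)·h.
- Mean stay, later-onset MODS: m + 1/r.
- Mean stay, all MODS: f·m + (1 − f)(m + 1/r).
- Mean stay, no MODS: 1/r.

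**Worked case, m = 8, f = 0.** q = 0.265. h = 0.265 × 0.125 / (0.875 × 0.735) = 0.0515. r = 0.125 + 0.875 × 0.0515 = 0.170, so 1/r = 5.9. Mean stay is 8 + 5.9 = 13.9 days with MODS and 5.9 without.

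**Results for m = 8.** Means come from the formulas. Median day of death comes from a simulation of 400,000 patients per row on the same assumptions.

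| Share of MODS cases present on day 1 | Mean stay, MODS v no MODS (days) | Median day of death, MODS v no MODS |
|---|---|---|
| 0% | 13.9 v 5.9 | 12 v 4 |
| 50% | 11.4 v 6.8 | 9 v 5 |
| 80% | 9.5 v 7.5 | 7 v 5 |
| 100% | 8.0 v 8.0 | 6 v 6 |

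For m = 5 the range runs from 8.7 v 3.7 to 5.0 v 5.0. For m = 12 it runs from 20.8 v 8.8 to 12.0 v 12.0. The ratio of means is about 2.4 when no case is present on day 1, and 1.0 when all are, whichever mean stay is assumed.

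**Would a test find it?** In simulated studies of 1346 patients, a Mann-Whitney test at 5% rejected in 97% or more with up to 80% of cases on day 1, in about half at 90%, and at about its nominal rate at 100%.

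**Proportion dying.** It was about 15% in both groups in every scenario. This check shows no bias in whether patients die, only in when.

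**Does the remedy work?** With MODS status taken at the end of day 3 among patients still in the unit, and stay counted from then, mean remaining stay was 8.0 v 8.0 days for m = 8. It was also equal in the two groups for m = 5 and m = 12.

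Organ-support days were not simulated. They cannot exceed the days in hospital, so the same direction is to be expected, but no size is claimed.

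**The case against.** The strongest reply is that the protocol never writes down a comparison of MODS with non-MODS patients on stay. The sentence about degrees of organ dysfunction is an example and names no dependent variable. The univariate comparisons that are spelled out are between age groups, and age is fixed at admission. The regression example treats MODS as the outcome. The mortality aims can be read as description, and an analysis plan that is not shown could deal with onset.

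Much of this stands. Relating MODS to stay or organ support is an inference from the listed outcomes. A reader might also infer that degree means the peak score over the whole stay, but the protocol does not say how degree is derived from daily scores. Nor does it support saying that patients must stay or survive for some time before they can be labelled: one score above 5 on day 1 is enough, and if all onset were on day 1 the artefact would vanish.

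Two things do not fall away. The synopsis puts comparison of more than two groups under secondary outcome analysis, and section 6 gives degrees of organ dysfunction as such a grouping, so some comparison of this kind is planned. The link between MODS and mode of death is a stated objective. For both, the protocol fixes a whole-stay status and lists only methods that cannot use onset time. An analysis plan that followed section 6 as written would carry the problem forward.

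**Conclusion.** The point holds in conditional form. Wherever stay, organ-support days or timing of death are related to MODS status, or to a degree taken over the whole stay, the named methods are exposed to immortal-time bias towards longer stay and later death.

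The size cannot be read from the protocol. On the assumptions above, the spurious difference in mean stay runs from about 8 days (13.9 v 5.9) to none (8.0 v 8.0), and the share of cases present on day 1 decides where it falls. At 80% it is still 2 days, and a study of this size would usually call it significant.

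Three stronger readings are not supported. The primary comparison of MODS proportions by age group does not use MODS as an exposure and is unaffected, as is its sample size. Secondary outcomes compared by age group are unaffected too. The proportion dying in hospital has not been shown to be biased.

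This is an inexpensive improvement to the analysis text, not a flaw in the design.

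**What to change.** Add to section 6 (Methods of analysis):

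- Where stay, organ-support days or timing of death are related to MODS, MODS enters as a time-varying covariate that switches on at the first day with a total SOFA above 5, with cause-specific models for death and for discharge.
- A landmark set in advance (for example MODS status by day 3 among patients still in critical care, with outcomes counted from then) is the simpler alternative. It is the natural form for organ-support days, which are a count.
- State how degree of organ dysfunction is derived from the daily scores and which outcomes it is compared on.
- Label as descriptive any comparison by ever-MODS or by a degree taken over the whole stay.

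No new data are needed: daily SOFA, lengths of stay and timing of death are already collected. The cost is the wording and modest extra programming. A landmark leaves out patients who die or are discharged before it, and it counts later-onset MODS as no MODS. That matters in a study interested in late death, so the time-varying model is preferred.

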Paper CRFs will be stored within a locked office in each centre (only accessible to the centre PI and data collectors) and then entered onto the password protected study website by QMUL research nurses.

A password protected coding log which will include identifiable patient data (name, address and date of birth) for patients who have consented to long term outcome follow-up. This will be transferred to [name] (CI) at the end of the in-hospital data collection period. At ten months after injury the NHS Health and Social Care Information Centre (NHS Spine) or patients General Practitioner (GP) will be contacted to ensure that the patient is still alive at this time point. This will avoid erroneous long term follow up and exposing relatives to undue distress. At 12 months post injury, the EQ5D and questionnaire will be administered to each participant who has provided informed consent.

	In critical care	At discharge from hospital	10 month post injury NHS spine check/GP check	12 months post injury
Enrolment	х			
CRF initiation	х			
Informed	х			
consent				
Daily SOFA score	х			
and outcomes				
recorded				
CRF completion		х		
Long term			х	х
follow up				

Schedule of Assessment

End of Study Definition

The study will be formally completed when 12 month follow up for all patients has been obtained and data analysis is complete.

Sample size:

We are planning a study of older patients (≥65 years) and younger (<65 years) controls. Prior research data suggest that the MODS rate among younger patients is 23% and for older patients is 33%. If the true MODS rate in older people is 0.33, we will need to include 259 older subjects and 414 younger subjects per year to be able to reject the null hypothesis that the prevalence of MODS for older and younger patients is equal (power 0.80, alpha 0.05). The total sample size for the two year period is 1346 (518 older patients and 828 younger controls). Each London MTC will aim to enroll:

130 older patients (>64 years) and 207 younger patients (<65 years).

Methods of analysis:

Statistical analysis will be performed using SPSS v.23 (IBM Corporation, Armonk, NY,USA). A p value of <0.05 is considered statistically significant for univariate analysis. De-identified data will be cleaned and categorical data formatted into binary fields for analysis. Normal distribution will be assessed with the Shapiro-Wilk test.

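### The MODS regression selects its covariates by significance, does not guarantee frailty a place, and does not require in-stay predictors to precede MODS

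*Protocol*

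**What the plan says.** Protocol section 6, Methods of analysis, describes the model: "Multivariable regression analysis will be used to determine statistically independent relationships between MODS and age plus other significant independent variables". The examples in brackets are "such as the effect of injury severity, blood transfusion, on the development of MODS". Binary outcomes get logistic regression, reported as adjusted odds ratios with 95% confidence intervals. The only significance threshold is p<0.05, which the section attaches to univariate analysis. The univariate tests it describes compare the two age groups.

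On frailty, section 4 (Introduction) states: "Therefore it may be that frailty rather than age increases the risk of MODS after severe injury". It then commits the study to finding how far MODS is related to ageing and to frailty. The data list in section 6 includes the Edmonton Frail Scale. The model description does not mention frailty.

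On timing, section 5 defines the primary outcome as MODS at any point in the critical care admission and sets an objective of finding predictors and risk factors for developing it. The section 6 data list includes daily lymphocyte and neutrophil counts, nutrition, and "Adverse events: Such as infection, delirium, stroke or cardiac dysfunction". Transfusion is not on that list, and age is collected in ranges. No section says that a predictor must be measured before MODS begins.

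**The concern.** Two features of the stated model bear on what its results would mean.

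**Selection.** If a covariate stays because it is significant, the adjusted age odds ratio answers a question that the data have picked. Its meaning shifts with the variables retained, and an interval computed as if the model had been fixed in advance is too narrow. Frailty matters most here because the study wants to separate it from age, yet the rule fixes only one of the two.

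**Timing.** Outcome and in-stay exposures share the same window. The Introduction itself describes the reverse direction: in older patients, lasting organ dysfunction is complicated by immune suppression and infection and lengthens the stay. A longer stay gives more days on which to be transfused or to record an abnormal count. A variable summarised over the whole stay can then be associated with MODS without contributing to it. The objective on predictors and risk factors is what is at stake.

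**Working it through.** **1. The plan's own figure.** Inputs from Sample size: rates 0.33 (older) and 0.23 (younger); "we will need to include 259 older subjects and 414 younger subjects per year"; "power 0.80, alpha 0.05". I assume a two-sided test, pooled variance and no continuity correction. The ratio is k = 414/259 = 1.598 and the pooled rate is (0.33 + 1.598 × 0.23)/2.598 = 0.268.

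n(older) = [1.96 × √((1 + 1/k) × 0.268 × 0.732) + 0.842 × √(0.33 × 0.67 + 0.23 × 0.77/k)]² / 0.10² ≈ 254, with 407 younger.

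That is within 3% of the stated 259 and 414, so the sample size is not in dispute.

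**2. Does the sample size force selection?** Expected MODS cases over two years = 518 × 0.33 + 828 × 0.23 = 170.9 + 190.4 ≈ 361. At ten events per parameter, that supports about 36 parameters. It does not force selection.

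**3. What selection can let in.** Assume each candidate is screened at p<0.05 and all are independent noise. The chance that at least one enters is 1 − 0.95^10 = 40% with 10 candidates and 1 − 0.95^20 = 64% with 20. The protocol does not state this screen, so these figures only illustrate.

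**4. Why frailty matters.** Assume the whole age effect runs through frailty, with prevalence 30–50% in older and 5–10% in younger patients, and risks set to give 33% and 23% overall. In 500 simulated studies per setting (518 older, 828 younger):

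| Model | Age OR | Age p<0.05 |
|---|---|---|
| Without frailty | about 1.65 | 97–98% |
| With frailty | 0.99–1.00 | 4–6% |

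In the same runs frailty passed a p<0.05 univariate screen every time.

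**5. Timing, by hand.** Assume an event unrelated to MODS with a constant 3% daily chance. The chance of at least one event in L days is 1 − 0.97^L.

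| Stay (days) | Chance | Odds |
|---|---|---|
| 5 (no MODS) | 14.1% | 0.1645 |
| 7 (MODS) | 19.2% | 0.2377 |
| 12 (MODS) | 30.6% | 0.4413 |

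Spurious OR for 5 v 7 days: 0.2377/0.1645 = 1.44. For 5 v 12 days: 0.4413/0.1645 = 2.68.

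**6. Timing, in the planned model.** This used logistic regression with age group and transfusion, where transfusion has no effect on MODS (300 simulated studies per row; stays and daily rates assumed).

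| Mean stay, MODS v none (days) | Daily chance | OR, any time in stay | OR, first day only |
|---|---|---|---|
| 6 v 4 | 5% | 1.57 | 0.97 |
| 8 v 4 | 5% | 2.20 | 0.98 |
| 12 v 4 | 5% | 3.73 | 0.99 |
| 8 v 4 | 10% | 2.48 | 1.00 |

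The any-time variable reached p<0.05 in 84–100% of runs. The variable with an equal early window did so in 4–7%.

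**The case against.** The strongest reply is that the protocol names a family of models with examples, and that a SAP, which is not at hand, may fix the covariates and exposure windows. That stands as far as it goes: a missing list or window would not be a finding on its own. But the wording on significant variables and the transfusion example without a time window are the protocol's own text, and a SAP that followed them would carry the problem over.

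Several stronger readings are tempting and should not be drawn:

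- **That MODS predictors will be screened univariately at p<0.05.** This is plausible but not stated. The threshold is given for univariate analysis, and the tests described compare age groups, not patients with and without MODS.
- **That frailty will be dropped.** The calculation does not show this. A frailty effect strong enough to explain the age difference passed the screen in every run. It could be lost if the effect were weaker or scores were missing. The defect is that its place is left to a p-value.
- **That infection will be used as a predictor.** Section 5 lists it as a secondary outcome, and the model description names only injury severity and transfusion. The 3% figures illustrate any in-stay event.
- **That everything needed is already collected.** Transfusion is not on the data list, and age is recorded in ranges.
- **That adjusting for transfusion is wrong in itself.** It is a coherent candidate given the objective on predictors. Whether it belongs in the model for age depends on which age effect is wanted.

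Daily recording is not a fault either. It is what makes correct timing possible.

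**Conclusion.** The point holds in two parts. First, the covariates are chosen by significance, the intervals ignore that choice, and frailty is not guaranteed in the model meant to separate it from age. This follows from the text, and the expected number of MODS cases removes any need for it. Second, in-stay exposures are set against MODS at any time in the same stay with no requirement on order, so consequences of MODS or of a longer stay could appear as its predictors.

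The direction of the timing bias follows from the protocol's own statement that MODS lengthens stay, but its size cannot be fixed from the documents. It ranged from an odds ratio of about 1.4 to 3.7 over the assumed stays and daily rates, and a smaller difference in stay gives a smaller bias. A reader might infer that the main result is at risk. It is not: the chi-squared or Fisher comparison of MODS proportions uses none of these covariates.

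**What to change.** In section 6, Methods of analysis, replace the phrase on other significant variables with a named set entered whatever the p-values: age (as collected), Edmonton frailty score, ISS, mechanism, co-morbidity, sex and centre.

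For any in-stay predictor (immune counts, nutrition, and transfusion if it is recorded), use only values from before MODS onset, over a comparable exposure window in patients with and without MODS. Both conditions are needed. Cutting at onset alone would give MODS patients fewer days in which to be exposed and could bias the estimate the other way.

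Report the age estimate both with and without these post-injury variables, so that the reader can see which age effect is meant.

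The cost is small: some non-significant terms stay in the model and there is a little more analysis work. The fixed set uses data already listed. Transfusion would have to be added to the data items, with its date, if it is to be used.

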3. SUMMARY/SYNOPSIS

Short Title	MODET			
Method	Multi-site prospective observational study			
Research Sites	Major Trauma Centres (MTC) within the Pan-London Major Trauma System: Royal London Hospital, Barts Health NHS Trust St Marys Hospital, Imperial College Healthcare NHS Trust Kings College Hospital, King's College Hospital NHS Foundation Trust St Georges Hospital, St George's University Hospitals NHS Foundation Trust			
Objectives/Aims	This study aims to: Identify the prevalence, severity and patterns of multiple organ dysfunction syndrome (MODS) Determine predictors and risk factors of developing MODS Identify age related characteristics that contribute to MODS Examine the mode of mortality associated with MODS Analyse the relationship between MODS and longer-term recovery and quality of life			
Number of	1346			
Participants/Patients				
Main Inclusion Criteria	Inclusion criteria: Adult patients (≥16 years of age) with multiple injuries admitted to adult critical care unit within the four London MTCs.			
Statistical Methods and Analysis	 Analysis populations: Patients who are greater than 64 years of age will comprise the older-age cohort and younger patients (controls) are defined as ≤64 years. Primary outcome analysis: Difference in proportion will be examined with chi squared or fishers exact tests. Secondary outcome analysis: Univariate analysis of variables between the two age groups will be conducted using unpaired students t-tests or Mann Whitney U tests. Analysis of more than two groups or variables will be conducted using ANOVA or Kruskal Wallis tests. 			
Proposed Start Date	1 st February 2017			
Proposed End Date	1 st May 2020			
Study Duration	Three years			

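### Stay and organ-support days are compared by age group with no rule for death, so the result mixes mortality with length of stay and can shrink, hide or reverse a true difference

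*Protocol*

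**What the plan says.** Study Objectives (section 5) lists the secondary outcomes as "in-hospital mortality, ventilator use, level of organ support, adverse events such as infection or stroke, critical care stay and total length of stay". In-hospital mortality therefore stands beside stay and support as a separate outcome.

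The data collection list in Methodology (section 6) records these outcomes as plain counts: "Total number of days on organ support (CTCOFR score" and "Length of stay: In critical care and total hospital stay". The same list includes "Mortality: Mode and timing".

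Under its secondary outcome analysis, the Synopsis (section 3) states: "Univariate analysis of variables between the two age groups will be conducted using unpaired students t-tests or Mann Whitney U tests". Methods of analysis (section 6) repeats these tests and adds the adjusted models: "Multivariate linear regression will be used to analyse continuous dependent variables and binary logistic regression for binary dependent variables".

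Ethics (section 9) keeps the de-identified data of patients who die in hospital. No section describes a survivor-only analysis, a support-free-days outcome, a ranking that includes death, or a competing-risk method.

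**The concern.** Death ends a stay and ends organ support. If the raw count is analysed in everyone, a patient who dies early contributes a small number, just like a patient who recovers fast. This would matter little if death were equally common in the groups compared. Here it is not expected to be: the Introduction (section 4) says that prolonged organ dysfunction in older patients extends hospital stay, and that MODS in older people carries higher mortality. The first lengthens raw stay in the older group and the second, in most circumstances, shortens it. A single mean or rank difference then describes neither. Adjusting with linear regression does not help, because the outcome itself carries the mixture. The same applies to any comparison of patients with and without MODS.

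At stake is whether the study can say if older patients stay longer. It could report no difference, or a shorter stay, when older survivors in fact stay longer.

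**Working it through.** **Inputs from the protocol.** Planned numbers are 518 older and 828 younger patients. Direction only: longer stay and higher mortality in older patients with MODS, with those deaths described as late (Introduction). The protocol has no figure of its own for stay, mortality or time to death, so there is nothing to reproduce on this point.

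**Assumed inputs.** Lognormal stay with log-SD 0.8; survivor medians 12.5 (older) v 10 days (younger); mortality 15-25% v 10%; lognormal death times, log-SD 0.8, with the median day varied.

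**Step 1, survivors.** The mean of a lognormal is median × exp(SD²/2), and exp(0.8²/2) = 1.377. The survivor difference is (12.5 − 10) × 1.377 = 3.44 days. Mann-Whitney detects it in about 99% of simulated studies.

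**Step 2, all patients, mortality 25% v 10%, death times not capped.** With deaths at median day m:

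- survivor part: (0.75 × 12.5 − 0.90 × 10) × 1.377 = 0.375 × 1.377 = 0.52 days
- death part: (0.25 − 0.10) × 1.377 × m = 0.207 × m days

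| Median day of death | Mean difference, all patients | Mann-Whitney significant (simulated) |
|---|---|---|
| 4 | 0.52 + 0.83 = 1.3 | 12-14% |
| 14 | 0.52 + 2.89 = 3.4 | 99.6% |
| 20 | 0.52 + 4.13 = 4.7 | 100% |

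The mean distortion vanishes at m = (3.44 − 0.52) / 0.207 ≈ 14 days and changes sign beyond that.

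**Step 3, death times capped at the stay the patient would otherwise have had, so death can only shorten it (simulated).**

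| Mortality | Median day of death | Mean difference | Significant |
|---|---|---|---|
| 25% v 10% | 4 | about 1.3 | about 11% |
| 25% v 10% | 10 | about 2.0 | about 75% |
| 25% v 10% | 15 | about 2.3 | about 93% |
| 20% v 10% | 4 | about 1.9 | about 45% |
| 15% v 10% | 20 | about 3.1 | about 99% |

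A repeat of these runs agreed to within a few points; the 11% came out at 8%. Under the cap the estimate stays below 3.4 days throughout, even where power recovers.

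**Step 4, can the direction reverse?** A second model used a median stay of 8 days in younger patients, 25% longer in older, log-SD 0.9, and exponential death times capped in the same way.

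- Mortality 30% v 10%, mean time to death 4 days: the median difference moves from +2.0 to −0.4 days, and older stays are significantly *shorter* in 19% of runs.
- Mortality 40% v 15%, same timing: −0.9 days and 71%.
- Mean time to death 15 days, at these two mortality settings: +0.8 and +0.5 days, with practically no reversals.
- No true difference in stay, mortality 30% v 10%: older patients appear significantly shorter in 50% (late deaths) to 99% (early deaths) of runs.
- Equal mortality of 10%: +1.7 to +1.8 days, so little is lost.

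**The case against.** **Timing of death.** The Introduction describes MODS deaths in older people as late and slow, while the strongest figures need deaths around day 4. This stands. A reader might infer from the 11-14% power that the plan *will* hide a longer stay. The documents do not support that: it is one unfavourable assumed case. With late deaths power is largely restored, and without the cap the distortion disappears or changes sign. What survives is that the size and even the direction of the bias depend on quantities the protocol does not give.

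**Is the method really fixed?** Stay is not named next to the tests, and the statement keeping deaths in the data is in the Ethics section rather than in an analysis-set definition. An analysis plan not seen here could add a death rule. Yet the Synopsis assigns the tests to the secondary outcome analysis, the linear model is assigned to continuous outcomes, and the outcomes are defined as raw days. Followed as written, this gives the mixed comparison.

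**Raw bed-days are legitimate for resource use.** True. Nothing in the protocol says that a short stay counts as good. But raw bed-days then answer a resource question, not whether older patients take longer to recover.

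**The remedy also mixes mortality with stay.** This stands. With equal survivor stays, an analysis of discharge alive that keeps deaths in the risk set finds slower discharge in older patients in 100% of runs at 25% v 10% mortality, and in 62% at 15% v 10%. The difference is that death then counts openly as not being discharged alive. The components must still be shown.

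**Normality testing.** A reader might extend the point to "Normal distribution will be assessed with the Shapiro-Wilk test". That does not follow: skewed stays would go to Mann-Whitney, which is suitable for skew, and at this sample size linear regression can estimate mean differences without normal data. The weakness is the handling of death, not the distribution.

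**Conclusion.** The point holds as a weakness in the secondary analyses. As written, the protocol compares raw stay and support days across age groups that it expects to differ in mortality, and no stated analysis accounts for death. The result can shrink, hide or reverse a true difference in stay.

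The size rests wholly on assumed inputs. Under the capped model a survivor difference of about 3.4 days becomes about 1.3 to 3.1 days. Power runs from about 11% (25% mortality in older patients, deaths at median day 4) to 99% (15% mortality, deaths at median day 20). Reversal appears only with larger mortality gaps and early deaths when older stays are truly longer. If there is no true difference in stay, a false shorter stay in older patients is common with late deaths too.

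It would be wrong to infer that the primary comparison of MODS rates is affected; it lies outside this point.

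**What to change.** Amend the Synopsis and Methods of analysis as follows.

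- **Critical care and hospital stay:** analyse as time to discharge alive with death as a competing event, and report the cumulative incidence of discharge alive and of death by age group. Use the matching regression for adjusted results in place of linear regression.
- **Organ support:** analyse as days alive and free of support to a fixed day stated in advance, with deaths ranked worst, by Mann-Whitney and, for adjustment, ordinal regression.
- **Beside both:** report in-hospital mortality, and the raw stay and support days split by survival status. Raw bed-days in all patients can be kept if labelled as resource use.

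The cost is wording and analysis code; the timing of death is already collected. The downside is that results become ratios or ranks rather than mean days, and that these measures combine mortality with stay. A worse result in older patients could then come from mortality alone, so the separate components are a necessary part of the report.
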